### 6.2.3.2 Early Termination at an Individual Study Center

At any time, the study can be terminated at an individual center if:

- The center cannot comply with the requirements of the protocol.
- The center cannot comply with GCP standards.
- The required recruitment rate is not met.

Should the study be prematurely terminated, all study materials (IMPs, etc.) must be returned to the Sponsor.

# 7 ASSESSMENTS AND METHODS

# 7.1 Demographic and Baseline Information

The following information will be recorded during the Screening Visit:

### 7.1.1 Demographic and baseline characteristics

The demographic and baseline characteristics are age, ethnic origin, height, weight, and Body Mass Index (BMI).

Blood type (ABO) will be documented. If not available, this will be tested.

CD4+ count will be determined.

The Hemophilia Joint Health Score (HJHS) will be documented.

Target joint(s) will be documented (defined as three or more spontaneous bleeding episodes into a single joint within 6 consecutive months preceding screening visit).

#### 7.1.2 Medical history and prior/concomitant medications

The medical history will be obtained by interviewing the patient. Records of past diseases and treatments (e.g., hospital discharge letters) will be obtained for the study files, if available.

ut written per Prior and concomitant medications, including FVIII treatment details in previous 6 months and bleeding frequency will be documented.

#### 7.2 **Efficacy Assessments**

#### 7.2.1 Assessments for Secondary Efficacy Endpoints

#### 7.2.1.1 Bleeding episode (BE) data to be documented

For any BE occurring during the study, the following data will be recorded:

- BE type (spontaneous, traumatic, postoperative, other)
- BE site •
- BE severity (minor, moderate, major, life-threatening)
- Date and time the BE first occurred or was first noticed
- Date and time the BE ended •
- Dates and times Nuwiq was injected, if applicable
- Nuwiq dose(s) and batch number(s)
- Assessment of the efficacy of treatment at the end of the BE; see below

All of these parameters will be documented by the patient (together with the investigator in case of on-site treatments) in the patient diary. Patients who experience a major or life-threatening BE should be treated at the study site.

### Definition of BE

If the treatment of a BE at one site is interrupted for more than 48 hours, the events are recorded as two separate BEs; if another than the original bleeding site is affected, the events are recorded as separate BEs at any time.

If there are several simultaneous bleeding sites, each bleeding site is recorded as a separate BE.

For certain major bleeding events, e.g., iliopsoas bleeds or bleeding into target joints, it may be necessary to continue treatment beyond the resolution of the acute phase to prevent recurrent hemorrhage. These additional infusions should be recorded in the diary (and eCRF) but will not be evaluated as treatments of the BE.

#### Assessment of the efficacy of treatment at the end of a BE

At the end of a BE, treatment efficacy will be assessed by the patient (together with the investigator in case of on-site treatment) using the following predefined criteria:

- Excellent: Abrupt pain relief and/or unequivocal improvement in objective signs of bleeding within approximately 8 hours after a single infusion
- Good: Definite pain relief and/or improvement in signs of bleeding within approximately 8–12 hours after an infusion, requiring up to 2 infusions for complete resolution
- Moderate: Probable or slight beneficial effect within approximately 12 hours after the first infusion, requiring more than 2 infusions for complete resolution
- None: No improvement within 12 hours, or worsening of symptoms, requiring more than 2 infusions for complete resolution

The proportion of BEs successfully treated with Nuwiq will be evaluated for all BEs together and by severity. All efficacy ratings assessed as either 'excellent' or 'good' will be considered 'successfully treated.'

### 7.2.1.2 FVIII:C plasma levels

Blood samples for the assessment of FVIII:C (one-stage and chromogenic assays) plasma levels will be taken at the following timepoints:

- Cohort 1: before injection of OCTA101 50 IU/kg sc, 0.5 h, 2 h, 4 h, 8 h, 24 h, 48 h, and 72 h after injection.
- Cohort 2: before injection of OCTA101 100 IU/kg sc, 0.5 h, 2 h, 4 h, 8 h, 24 h, 48 h, ٠ 72 h and 96 h after injection.
- Cohort 3: FVIII: C only, before injection of Nuwig 50 IU/kg iv, 0.5 h, 2 h, 4 h, 8 h, 24 h, 48 h, and 72 h after injection.
- Cohort 3: before injection of OCTA101 50 IU/kg sc, 2 h, 4 h, 8 h, 12 h, 24 h, 48 h, and 72 h after injection.
- Cohort 5: before injection of OCTA101 20 IU/kg sc, 2 h, 4 h, 8 h, 12 h, 24 h, 48 h, and 72 h after injection.
- Cohort 5: before injection of OCTA101 40 IU/kg sc, 2 h, 4 h, 8 h, 12 h, 24 h, 48 h, and 72 h after injection.
- Cohort 5: before injection of OCTA101 60 IU/kg sc, 2 h, 4 h, 8 h, 12 h, 24 h, 48 h, and 72 h after injection.
- Cohort (1, 2, and 3 daily sc injections for 3 months: before injection of OCTA101)25 TU/kg sc and 3 and 6 h after injection, for the first injection and at 0.5, 1, 2 and 3 months thereafter.
- Cohort 1 and 2 patients PK assessment following 3-month daily prophylaxis: before injection of OCTA101 50 IU/kg sc, 2 h, 4 h, 8 h, 12 h, 24 h, 48 h, and 72 h 96 h, and 120 h after injection.
- Property of Cohort 6 – daily sc injections for 6-7 months: before injection of OCTA101 12/25 IU/kg sc (and probably 40 IU/kg) and 8 h after injection, for the first injection and at 0.5, 1, 2, 3, 4, 5 and 6 months thereafter in each dosing period. Samples will be shipped to the central laboratory for one-stage and chromogenic assay assessments (see Section 7.3.5).

sion

#### 7.3 Safety Assessments

#### 7.3.1 Assessments for Safety Endpoints

Any of the following drug safety information shall be collected:

- Adverse events (AEs) and serious adverse events (SAEs) associated with the administration of IMP (for definitions and reporting requirements, see Sections 7.3.2, 7.3.3, and 7.3.4)
- Drug overdose, interaction, medication error, lack of efficacy, and post-study SAEs (see written Section 7.3.7)

#### 7.3.2 Adverse Events (AEs)

#### 7.3.2.1 Definitions

- Adverse event (AE): An AE is any untoward medical occurrence in a study patient receiving an IMP and which does not necessarily have a causal relationship with this treatment. An AE can therefore be any unfavorable and unintended sign (including an abnormal laboratory finding), symptom, or disease temporally associated with the use of an IMP, whether or not related to the IMP.
- Adverse drug reaction (ADR): An ADR is any noxious and unintended response to an IMP related to any dose. The phrase 'response to an IMP' means that a causal relationship between the IMP and an AE carries at least a reasonable possibility, i.e., the relationship cannot be ruled out.
- Other significant AEs: Any marked laboratory abnormalities or any AEs that lead to an intervention, including withdrawal of drug treatment, dose reduction, or significant additional concomitant therapy.
- Withdrawal due to AE/ADR: AE/ADR leading to discontinuation of treatment with IMP. Any such events will be followed up by the Investigator until the event is resolved or until the medical condition of the subject/patient is stable. All follow-up information collected will be made available to the Sponsor.

# 7.3.2.2 Collection of AEs

The condition of the patient will be monitored throughout the study. At each visit, whether scheduled or unscheduled, AEs will be elicited using a standard nonleading question such as "How have you been since the last visit/during the previous study period?" In addition, the Investigator will check the patient diaries (if applicable) for any documented event.

Any AE or ADR which occurs during the study will be noted in detail on the appropriate pages of the eCRF. If the patient reports several signs or symptoms representing a single syndrome or diagnosis, the diagnosis should be recorded in the eCRF. The Investigator will grade the severity of all AEs or ADRs (mild, moderate, or severe), the seriousness (non-serious or serious), and the causality as defined in Sections 7.3.2.3, 7.3.3, and 7.3.2.4. The Sponsor is responsible for assessing the expectedness of each ADR (expected or unexpected) as defined in Section 7.3.2.5.

In the event of clinically significant abnormal laboratory findings, the tests will be confirmed, and the patient followed up until the laboratory values have returned to normal and/or an adequate explanation for the abnormality has become available.

Diseases, signs and symptoms, and/or laboratory abnormalities already present before the first administration of IMP will not be considered AEs unless an exacerbation in intensity or frequency (worsening) occurs.

The Investigator will provide detailed information about any abnormalities and about the nature of and reasons for any action taken as well as any other observations or comments that may be useful for the interpretation and understanding of an AE or ADR.

#### 7.3.2.3 Severity of AEs

The intensity/severity of AEs will be graded as follows:

- Mild: an AE, usually transient, which causes discomfort but does not interfere with the patient's routine activities
- **Moderate:** an AE that is sufficiently discomforting to interfere with the patient's routine activities
- Severe: an AE that is incapacitating and prevents the pursuit of the patient's routine activities

The grading of an AE is up to the medical judgement of the Investigator and will be decided on a case-by-case basis.

#### 7.3.2.4 Causality of AEs

Property

The relationship of AEs to the administered IMP will be assessed by the Investigator:

- **Probable:** reports including good reasons and sufficient documentation to assume a causal relationship, in the sense of plausible, conceivable, likely, but not necessarily highly probable. A reaction that follows a reasonable temporal sequence from administration of the IMP; or that follows a known or expected response pattern to the suspected medicine; or that is confirmed by stopping or reducing the dosage of the medicine and that could not reasonably be explained by known characteristics of the patient's clinical state.
- **Possible:** reports containing sufficient information to accept the possibility of a causal relationship, in the sense of not impossible and not unlikely, although the connection is uncertain or doubtful, for example because of missing data or insufficient evidence. A reaction that follows a reasonable temporal sequence from administration of the IMP; that follows a known or expected response pattern to the suspected medicine; but that could readily have been produced by a number of other factors.
- Unlikely: reports not following a reasonable temporal sequence from IMP administration. An event which may have been produced by the patient's clinical state or by environmental factors or other therapies administered.
- Not related (unrelated): events for which sufficient information exists to conclude that the etiology is unrelated to the IMP.
- **Unclassified:** reports which for one reason or another are not yet assessable, e.g., because of outstanding information (can only be a temporary assessment).

#### 7.3.2.5 Classification of ADRs by Expectedness

ADRs will be classified by the Sponsor as either expected or unexpected:

- **Expected:** an ADR that is listed in the current edition of the Investigator's Brochure.
- ithout written permission. • Unexpected: an ADR that is not listed in the current edition of the Investigator's Brochure, or that differs because of greater severity or greater specificity.

#### 7.3.2.6 Outcome of AEs

The outcome of all reported AEs has to be documented as follows:

- 1. Recovered, resolved
- 2. Recovering, resolving
- 3. Not recovered, not resolved
- 4. Recovered, resolved with sequelae
- 5. Fatal
- 6. Unknown

NOTE: A patient's death per se is not an event, but an outcome. The event which resulted in the patient's death must be fully documented and reported, even in case the death occurs within 4 weeks after IMP treatment end and regardless of whether or not it is considered treatmentrelated.

#### 7.3.2.7 Action(s) taken

AEs requiring action or therapy must be treated with recognized standards of medical care to protect the health and well-being of the patient. Appropriate resuscitation equipment and medicines must be available to ensure the best possible treatment in an emergency situation.

The action taken by the Investigator must be documented:

#### a) General actions taken in the event of an AE

- None
- Medication (other than IMP) or other (e.g., physical) therapy started
- Test performed
- Other (to be specified)

#### b) IMP-related actions taken in the event of an AE

None

Property

- Product withdrawn
- Dose reduced
- Dose increased

The Investigator will follow up on each AE until it has resolved or until the medical condition of the patient has stabilized. Any relevant follow-up information will be reported to the Sponsor.

#### 7.3.3 Serious Adverse Events (SAEs)

A serious AE (SAE) is any untoward medical occurrence that at any dose:

- results in death,
- is life-threatening (see below),
- requires hospitalization or prolongation of existing hospitalization,
- results in persistent or significant disability/incapacity,
- is a congenital anomaly/birth defect, •
- is another important medical event.

MISSION **NOTE:** The term 'life-threatening' refers to an event in which the patient was, in the view of the reporting Investigator, at immediate risk of death at the time of the event; it does not refer to an event which may hypothetically have caused death had it been more severe.  $\bigcirc$ 

In deciding whether an AE/ADR is serious, medical judgment should be exercised. Thus, important AEs/ADRs that are not immediately life-threatening or do not result in death or hospitalization but may jeopardize the patient or may require intervention to prevent one of the other outcomes listed in the definitions above should also be considered serious.

One such 'important medical event' is the development of FVIII inhibitors. Another is the suspected transmission of an infectious agent. These events, therefore, have to be reported as SAEs.

A suspected virus transmission means that virus antigen has been detected in the patient. The passive transmission of antibodies alone does not constitute a suspected virus transmission.

#### 7.3.4 SAE Reporting Timelines

All SAEs, whether or not they are suspected to be related to study treatment, are to be reported immediately by telephone, fax, or email to the Clinical Project Manager or designee:

#### Waivers the from SAE Reporting Requirement

Waivers from the SAE reporting requirement include surgeries that are elective or permission prolongations of existing hospitalizations for economic or social, but not medical, reasons. Such surgeries or prolongations of hospitalizations should not be considered SAEs.

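### The SAE waiver for elective surgery is not limited to surgery planned before entry, so some on-treatment hospitalizations may go unreported as serious

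*Protocol*

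**What the plan says.** Protocol Section 7.3.3 lists the seriousness criteria. One is that the event "requires hospitalization or prolongation of existing hospitalization". The criterion has no exception for planned or elective admission. The section adds that "In deciding whether an AE/ADR is serious, medical judgment should be exercised", and it names FVIII inhibitor development as an event that must always be reported as an SAE.

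Section 7.3.4 attaches the reporting duty to SAE status: "All SAEs, whether or not they are suspected to be related to study treatment, are to be reported", and immediately.

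The paragraph on waivers that follows has two sentences. The first sets the scope: "Waivers from the SAE reporting requirement include surgeries that are elective or" "prolongations of existing hospitalizations for economic or social, but not medical, reasons". The second sets the effect: "Such surgeries or prolongations of hospitalizations should not be considered SAEs".

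Section 7.3.2.2 deals with conditions present before first IMP. They "will not be considered AEs unless an exacerbation in intensity or frequency (worsening) occurs".

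**The concern.** A waiver of this kind usually serves to keep out admissions that say nothing about the study drug, such as an operation already arranged when the patient enrolled. The wording here goes further. The only test for surgery is that it is elective, a word that ordinarily means scheduled rather than emergency. Nothing is said about when the surgery was planned, or whether the condition behind it is new or has worsened on treatment. The second sentence also does more than excuse a form: it removes the SAE classification.

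This is a first-in-human study whose primary objective is safety, with adverse events as a primary endpoint. SAE status decides three things: immediate reporting to the sponsor (Section 7.3.4), a place in the serious-AE tables (protocol Section 9.2.3; SAP Section 8.8.3 for Cohorts 1, 2, 3 and 5), and a possible unscheduled visit (Section 6.1.10).

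Surgery during the study is foreseeable. Section 7.2.1.1 provides for postoperative bleeds, and the exclusion criteria in Section 4.1.2 do not rule out patients with surgery in prospect. Two conditions that could lead to scheduled surgery also matter for this product: joint deterioration on daily prophylaxis, and the lasting tissue changes that Section 1.5 mentions for repeated subcutaneous injection at one spot.

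**Working it through.** No arithmetic applies, because the point rests on wording. The check is to follow one case through the provisions in turn.

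**Case (hypothetical).** A patient's joint worsens some months after the first dose of IMP. An operation is scheduled, and the patient is admitted for it.

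| Step | Provision | Result |
|---|---|---|
| 1. Is it an AE? | Section 7.3.2.2 | Yes. A pre-existing condition counts once it worsens, and a new condition counts in any event. |
| 2. Does it meet a seriousness criterion? | Section 7.3.3 | Yes, if the worsened condition requires the admission. The criterion has no elective exception. |
| 3. Does the waiver apply? | Waiver after Section 7.3.4 | Yes on its face. The surgery is elective, and no other condition is set. |
| 4. Must it be reported immediately? | Section 7.3.4 | Unclear. The duty covers SAEs; step 2 says it is one and step 3 says it is not. |
| 5. Where is it tabulated? | Protocol Section 9.2.3; SAP Section 8.8.3 | In the all-AE table either way. Inclusion in the serious table depends on step 4. Under the SAP it may fall in the non-serious table instead. |

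Steps 2 and 3 give opposite answers for the same admission, and neither document says which prevails.

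**Is the limit stated elsewhere?** Neither the protocol nor the SAP defines elective surgery, ties the waiver to a date of planning, or excludes conditions that began or worsened after first IMP.

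**Does the restriction on reasons cover surgery?** The phrase about economic or social reasons follows the prolongations and reads naturally with them alone. If it also governed the surgeries, medically indicated surgery would fall outside the waiver and the conflict would largely disappear. The sentence can be read that way, but less naturally.

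**What does the waiver leave untouched?** It names the surgery, not the condition that led to it. That condition can still be serious through another criterion in Section 7.3.3, such as lasting disability or an important medical event. FVIII inhibitors are SAEs whatever the waiver says. The toxicity definitions in Section 3.2 also stand: they count an indicated hospitalization towards severe toxicity, so a related event could count as severe for a dose-limiting toxicity and yet be handled as non-serious.

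**The case against.** The strongest reply is that a waiver is by nature an exception to the hospitalization criterion, and that this one exempts a procedure rather than a diagnosis. On that reading the investigator still assesses the underlying condition under Section 7.3.3, using medical judgment, and nothing of substance is lost. This may well be what was intended. But the text does not say so, and the route it leaves open is discretionary, while the waiver gives a flat instruction.

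The second reply is that the information is captured elsewhere, and much of this stands:

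- Local injection site reactions are a primary endpoint in their own right and are rated after each injection (Section 7.4.1).
- Joint score and target joints are assessed in Cohort 6 at screening, Month 6 and the final visit (Flow Chart 9), and the joint bleeding rate is a secondary endpoint.
- AEs that lead to an intervention are classed as other significant AEs (Section 7.3.2.1).
- Dose-limiting toxicities are not affected by the waiver.

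These routes keep the event in the data. They do not restore its SAE classification or its immediate report.

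A reader might also infer that Section 7.3.2.2 contradicts the waiver. It does not. That section decides whether a pre-existing condition is an AE, and the waiver decides whether an elective surgery is an SAE. A worsened joint can be an AE while the operation on it is waived. The conflict is with the hospitalization criterion in Section 7.3.3 alone.

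**Conclusion.** The point holds as a wording conflict with a limited effect. The waiver covers elective surgery without restriction and removes SAE status, which cuts across the hospitalization criterion in Section 7.3.3. An admission for elective surgery on a condition that arose or worsened after first IMP may therefore go unreported as an SAE and be missing from the serious-AE tables.

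Two stronger readings are not supported. A reader might conclude that every such event is lost as serious. The documents do not show this, because the condition remains an AE and may qualify on another criterion. A reader might also turn one missed event into a percentage of Cohort 6. The documents record no elective surgeries and give no expected rate, so such a figure would describe one hypothetical event. Its denominator is not fixed either: Section 3.2 plans at least 16 evaluable patients with around 18-20 starting, and the safety set takes everyone dosed. The size of any undercount cannot be estimated.

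The conclusion assumes that elective has its ordinary meaning of scheduled, and that the restriction to economic or social reasons applies to prolongations only. Nothing here bears on dosing or on the primary endpoint definitions. The priority is low, but the correction is cheap and protects safety reporting.

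**What to change.** Reconcile the waiver with Section 7.3.3 in three steps:

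1. Limit the waiver to hospitalization for surgery planned before informed consent, for a condition that has not worsened since the first dose of IMP. Leave the part on prolongations for economic or social reasons as it is.
2. State that a new or worsened condition leading to hospitalization is assessed and reported under Section 7.3.3, whether or not the surgery is elective.
3. Check the hospitalizations and surgeries already recorded, in all cohorts, against the clarified rule, and correct the seriousness classification where needed before the serious-AE tables are produced.

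The cost is one or two sentences in the protocol and a short check at a single center. The downside is a few more SAE forms and a possibly higher SAE count. The analysis methods do not change.

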#### 7.3.5 Laboratory Tests

#### 7.3.5.1 Local Laboratory

The routine safety laboratory tests (Hematology: red blood cell count, white blood cell count, hemoglobin, hematocrit, platelet count, CD4+ count. Clinical chemistry: total bilirubin, ALT, AST, urea, serum creatinine, lactate dehydrogenase) will be done by the local laboratory. The methods of determination and normal ranges for each parameter will be provided in the clinical study report.

